4.1.2 Hypotheses

To control the overall type I error rate at 2.5% one-sided, the significance level will be adjusted for one interim analysis of efficacy performed by the DMC (Section 5). For the

primary endpoint the following null hypothesis will be tested at the 2.496% one-sided significance level

$$H_0: \text{HR [dapagliflozin:placebo]} \geq 1$$

versus the alternative hypothesis

$$H_1: \text{HR [dapagliflozin:placebo]} < 1$$

The secondary endpoints included in confirmatory statistical testing using a closed testing procedure (Section 4.1.3) will be based on similar one-sided alternative hypotheses for the respective treatment difference. The significance level will be re-calculated based on the exact proportion of primary endpoints included in the interim analysis and may be marginally adjusted (Section 5).

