4.1.3 Confirmatory testing procedure

A closed testing procedure including a pre-specified hierarchical order of the primary and secondary endpoints will be utilized. The Type I error will be controlled at a one-sided 0.02496 level for multiplicity across primary and secondary endpoints and in consideration of the planned interim analysis. Statistical significance will be assessed in the pre-specified order of the endpoints as specified in Section 1.1.1 and 1.1.2. The testing procedure will continue down the hierarchy if the preceding endpoint is rejected at a one-sided 0.02496 level and will stop if the null hypothesis for the preceding endpoint is not rejected at a one-sided 0.02496 level.

If the study is stopped in the efficacy interim analysis (Section 5), testing of secondary endpoints will continue down the hierarchy at one-sided significance level 0.001.

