- Within subject recurrent HF hospitalizations and CV death are correlated events. This correlation varies from subject to subject. To account for this correlation, the hazard function of recurrent HF hospitalizations and hazard function of CV death are modeled by a joint a subject specific random frailty term which follows a gamma distribution with unit mean and unknown variance.
- Censoring (including non-CV death) is noninformative, in particular it does not depend on random frailty.

Estimation in the frailty proportional hazards model will be done using Gaussian quadrature approach (Liu and Huang 2008, Lu and Liu 2014, SAS Institute Inc. 2018). Since SAS PROC NLMIXED supports only normal distributions, a probability integral transformation to generate numbers from a gamma distribution will be used (Nelson et al 2006) following Liu and Huang 2008.

Additionally, non-parametric estimates of the marginal mean of the cumulative number of recurrent HF hospitalization rates over time will be calculated allowing for death as terminal event, and the estimates will be plotted (Ghosh and Lin 2000). The estimation will be done in SAS using the PROC PHREG and by treating the situation as competing risks with several records per subject (Andersen et al 2019)

4.2.4.2 Analysis of change from baseline at 8 months in the KCCQ total symptom score

Hypothesis testing

The composite rank-based endpoint representing the patients' vital status at 8 months and the change from baseline to 8 months in TSS in surviving patients, as defined in Section 3.2.3, will be analysed using the rank ANCOVA method (Stokes et al 2012) to test the null hypothesis of no differences in the distributions of ranked outcomes between the two treatment groups. Analysis will be stratified by T2D status at randomisation, and adjusted for the baseline TSS value as follows.

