First the change from baseline to 8 months in TSS and vital status at 8 months, as well as values of the baseline TSS covariate will be transformed to standardized ranks, using fractional ranks and mean method for ties. Ranking for the composite endpoint will be done so that patients who died prior to the 8-month assessment are assigned the worst ranks within each stratum. Among the deceased the relative ranking will be based on their last value of change from baseline in TSS while alive before deriving fractional ranks. Then, separate regression models will be fit to the ranked data for each randomization stratum using a regression model for the ranked composite variable as dependent variable, adjusting for the ranked baseline covariate. Residuals from this regression model will be captured for further testing of differences between treatment groups. The Cochran-Mantel-Haenszel (CMH) test, stratified for the T2D status at randomization, using the values of the residuals as scores will be used to compare treatment groups.

Responses missing for reasons other than death will be imputed as described in section 'Handling of missing data'.

The p-value from the CMH test of treatment effect at 8 months will be used for the confirmatory statistical testing of the 3rd secondary endpoint in the multiple testing procedure described in section 4.1.3

Estimation of treatment effect

Win ratio:

For a summary statistic that uses the same ranking as that used in the hypothesis test, but has a clinical interpretation, the win ratio (WR) and the corresponding 95% confidence interval (Wang and Pocock 2016) will be reported. It is noted that the WR differs from the statistic used for hypothesis testing, so that exact consistency is not expected between these two analyses, e.g. on rare occasions, the confidence interval for WR could exclude unity while the pre-planned hypothesis test could be non-significant, or the hypothesis test could be

significant with the confidence interval for WR including unity. Formal inference for the superiority of the treatment over control will be made only from the preplanned hypothesis test.

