The win ratio represents the odds of having a more favourable outcome versus a less favourable outcome when assigned to the dapagliflozin 10 mg treatment group as opposed to placebo. More specifically, each patient in the dapagliflozin group is compared with each patient in the placebo group and each pair is labelled as “winner”, “loser”, or “tie”, depending on whether the patient on dapagliflozin has a more favourable, less favourable, or the same outcome, respectively, with respect to the composite ranked endpoint compared to the patient on placebo. Win ratio is defined as the ratio of the number of “winner” pairs to the number of “loser” pairs for the dapagliflozin arm. If the estimated win ratio is greater than 1 then the treatment effect is estimated to be in favour of dapagliflozin.

The win ratio statistic adjusted for the randomization stratification factor and baseline TSS will be obtained using the methodology in

Koch et al 1998, Kawaguchi et al 2011 for the stratified Mann-Whitney estimators for the comparison of two treatments with randomization-based covariance adjustment. The win ratio statistic will be calculated as Mann-Whitney odds, i.e., $WR = MW / (1 - MW)$, where MW is the adjusted Mann-Whitney estimate. This transformation is monotonous in the domain of the Mann-Whitney estimate. The 95% confidence interval for the win ratio will be obtained by transforming the bounds of the confidence interval (

Koch et al 1998) for the Mann-Whitney estimate, using the same transformation as for the win ratio.

Responder analysis:

Number and percentage of patients in each treatment group will be summarized across the following categories:

5 point improvement from baseline to 8 months in TSS vs no significant improvement:

- Change from baseline in $TSS \geq 5$ points, vs
- Death prior to the 8 months assessment or change from baseline in $TSS < 5$ points.

5 point deterioration from baseline to 8 months in TSS vs no significant deterioration:

- Death prior to the 8 months assessment or change from baseline in $TSS \leq -5$ points, vs
- Change from baseline to 8 months in $TSS > -5$ points.

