If a patient had a baseline value of $TSS \geq 95$ points, ie near the “ceiling”, they will be defined as having a 5 point improvement only if they had $TSS \geq 95$ points at 8 months. Similarly, if a patient had a baseline value of $TSS \leq 5$ points, ie near the “floor”, they will be defined as having a 5 point deterioration only if they had $TSS \leq 5$ points at 8 months.

The proportion of TSS responder categories will be compared between treatment groups using a logistic regression model including treatment group, stratification variable (T2D at randomisation) and baseline TSS value. The observed number of and proportion of TSS responders, odds ratio between treatment groups and its 95% confidence interval and corresponding 2-sided p-value estimated from each imputed dataset will be combined using Rubin's rule, and the combined results will be presented.

Additional responder analysis will be performed in the same way as for 5 points improvement and deterioration described above, using the thresholds of clinically meaningful within-patient change from baseline TSS derived from anchor-based analyses (10 point improvement, 10 point deterioration, 15 point improvement; Appendix B Section 8.2), with "ceiling" and "floor" values handled consistently.

Empirical cumulative distribution function (eCDF) plots will be presented by treatment group to summarize the distribution of change from baseline to 8 months in TSS values, where patients who die prior to the 8-month assessment will be represented with the value of -101 (a value below the worst possible change from baseline).

Handling of missing data

The number of patients with missing vital status at 8 months is expected to be negligible. If some patients are LTFU or patients who withdrew consent have unknown vital status, the main analysis will be done with these patients assigned the worst ranks (same as deaths).

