- In the analysis of rank ANCOVA, the CMH test statistic used for the hypothesis test has a chi-square distribution. In order to apply Rubin’s combination rule, which assumes approximate normal distribution of the statistics being combined, a normalizing Wilson-Hilferty transformation will be applied to the CMH test statistics from each imputed dataset (Ratitch et al 2013). The standardized transformed statistic will be computed as follows:

$$st_{wh_cmh}^{(m)} = \frac{\sqrt[3]{\frac{cmh^{(m)}}{df} - \left(1 - \frac{2}{9 \times df}\right)}}{\sqrt[3]{\frac{2}{9 \times df}}}$$

where $cmh^{(m)}$ is the CMH statistic from the m^{th} imputed dataset and df is the number of degrees of freedom associated with the statistic (in this case equal to 1). The transformed statistics are approximately normally distributed with a mean of 0 and variance of 1 and can be combined using Rubin’s rule.

- For the estimation of the win ratio, a combined Mann-Whitney estimate (MW) and its standard error ($SE(MW)$) will first be obtained by applying Rubin’s rule to the corresponding estimates from multiple imputed datasets. Then the win ratio and its 95% confidence interval will be obtained based on the combined Mann-Whitney estimate and its standard error as previously described.
- For the summaries of number and percentage of subjects in the categories of significant improvement and deterioration from baseline, as discussed in the “Estimation of treatment effect” sub-section above, the average number and percent of subjects in each category across all multiple imputed datasets will be reported. The TSS responder analyses will use the imputation datasets created for the main analysis. Therefore, deaths will be defined as non-responders, and responder status will be determined based on the imputed TSS values for the patients who have missing TSS due to reasons other than death.

Supportive analyses and sensitivity analyses

The number and percent of patients who die prior to the 8-month assessment will be summarized by treatment group.

Descriptive statistics of scores and change from baseline at 4, and 8 months will be presented for total symptom score, overall summary score, clinical summary score and domains (Physical limitation, symptom stability, symptom frequency, symptom burden, quality of life, self-efficacy and social limitation).

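### The confirmatory KCCQ p-value comes from an unsigned chi-square, and section 4.2.4.2 has no step that turns it into the one-sided 0.02496 test the hierarchy requires

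*SAP*

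**What the plan says.** Section 4.1.2 says that the tests of the secondary endpoints "will be based on similar one-sided alternative hypotheses for the respective treatment difference". Section 4.1.3 adds: "The testing procedure will continue down the hierarchy if the preceding endpoint is rejected at a one-sided 0.02496 level". After a stop at the interim analysis the one-sided level is 0.001.

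The KCCQ total symptom score is the third secondary endpoint, ahead of the renal composite and all-cause death. Section 4.2.4.2 specifies a rank ANCOVA "to test the null hypothesis of no differences in the distributions of ranked outcomes between the two treatment groups", which is a non-directional null. It continues: "The p-value from the CMH test of treatment effect at 8 months will be used for the confirmatory statistical testing". Under its missing-data heading it says that "the CMH test statistic used for the hypothesis test has a chi-square distribution", with 1 degree of freedom. The statistic from each imputed dataset is transformed by Wilson-Hilferty, treated as approximately standard normal, and pooled by Rubin's rule.

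On direction, the section says of the win ratio: "If the estimated win ratio is greater than 1 then the treatment effect is estimated to be in favour of dapagliflozin". It also says: "Formal inference for the superiority of the treatment over control will be made only from the preplanned hypothesis test". The responder analysis in the same section is labelled, with "95% confidence interval and corresponding 2-sided p-value estimated from each imputed dataset". The confirmatory CMH p-value carries no such label.

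**The concern.** A 1-df CMH statistic is the square of a signed quantity, so equal effects for and against dapagliflozin give the same value. The sign is lost in each imputed dataset, before pooling. The pooled result then resembles a z-score, but its upper tail means a large difference in either direction. Its lower tail means no difference, not harm: at CMH = 0 the standard transform equals about -1.65.

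The section does not name a tail, require the estimate to favour dapagliflozin, halve the p-value or double the level. Followed step by step, it does not produce the test that 4.1.3 declares. The p-value decides the KCCQ claim and gates two further endpoints. The question arises only if the primary and the first two secondary endpoints have already succeeded.

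**Working it through.** **Inputs from the SAP.** One-sided level 0.02496 at the final analysis and 0.001 at the interim, at 75% of events (1.4, 4.1.3, 5). CMH statistic with 1 df, Wilson-Hilferty transform, Rubin's rule (4.2.4.2).

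**The plan's own level reproduces.** Solve P(Z1 > 3.0902 or Z2 > c) = 0.025 with correlation √0.75. The final one-sided level is 0.024962, which matches 0.02496.

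**Cut-offs.** Write CMH = Z². The standard transform at 1 df is w = (CMH^(1/3) − 7/9) / √(2/9). An upper-tail p-value below a means CMH > x, with x = (7/9 + z_a·√(2/9))³. Under the null, the error for benefit is P(Z > √x).

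- a = 0.02496: z = 1.9606, so x = (0.7778 + 1.9606 × 0.4714)³ = 4.93, √x = 2.221, error for benefit 1.32%, and the same for harm.
- a = 0.04992 (twice the level): z = 1.6456, so x = 3.75, √x = 1.936, error for benefit 2.64% once the favourable direction is required.

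| Reading of the pooled p-value | Rejects at CMH above | Error for benefit | With exact chi-square tails |
|---|---|---|---|
| Upper tail against 0.02496, no direction check | 4.93 | 1.32% | 5.03; 1.25% |
| Two-sided p of the transformed z against 0.02496 | 6.18 | 0.65% | not applicable |
| Half the upper tail against 0.02496, favourable direction | 3.75 | 2.64% | 3.84; 2.50% |
| Early stop: upper tail against 0.001, no direction check | 11.16 | 0.042% | 10.83; 0.050% |
| Early stop: half the upper tail against 0.001, favourable direction | 9.73 | 0.091% | 9.55; 0.100% |

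**Two examples.**
- Favourable Z = 2.0: CMH is 4.0. The one-sided p is 0.0228, which passes 4.1.3. The transformed upper-tail p is 0.0429, which fails 0.02496.
- Z = −2.5, favouring placebo: CMH is 6.25 and the transformed upper-tail p is 0.0120. Read literally this rejects, although the one-sided p for benefit is 0.994.

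**Power.** The SAP gives no KCCQ effect or power, so 80% and 90% are assumed as references. The drift is 1.9606 + 0.8416 = 2.802 for 80% and 1.9606 + 1.2816 = 3.242 for 90%. With the cut-off at 2.221, power is Φ(0.582) = 72.0% and Φ(1.022) = 84.7%.

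**After pooling.** The SAP passages used do not give a number of imputations or a fraction of missing information, so both are assumed: 20 imputations with 5, 10 and 15% missing information, and 100 imputations with 5 and 15%.

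| Method | Error for benefit | Power (80% / 90% reference) |
|---|---|---|
| Signed square root, one-sided | 2.5% | 79.6–80.1% / 89.7–90.0% |
| Transform against 0.02496 | 1.3–1.4% | 71.6–72.1% / 84.3–84.7% |
| Transform at twice the level, with direction check | 2.6–2.7% | 80.2–80.7% / 90.1–90.4% |

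A separate run with 50 imputations and 5, 10 and 20% missing information gave 1.2–1.4% for benefit and 1.3–1.4% for harm on the direct comparison, and 2.5–2.8% with halving and a direction check.

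**The case against.** The strongest answer is that the governing rule is already in the plan. Sections 4.1.2 and 4.1.3 call for one-sided alternatives, 4.2.4.2 speaks of superiority over control, and the win ratio paragraph says which direction is favourable. A statistician reading these together would halve the p-value and check the direction. This stands: the defect is a missing rule, not an unusable test. A reader might infer that the endpoint has lost power or that false claims of benefit are inflated. The documents support neither. The power loss follows only from a direct comparison that 4.1.3 itself argues against, and that comparison is conservative for benefit.

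Nor is the missing label peculiar to KCCQ. The Cox p-value in 4.2.3 rests on a score statistic, which in chi-square form is equally unsigned, and it too has no sidedness label. A sharp contrast with the Cox analyses would be unfair. What is specific here is that an unsigned quantity is transformed to look like a z-score and pooled in that form, while formal inference is confined to that test.

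A reader might also infer that the printed transformation is wrong, because the available text shows cube roots where the standard form has none. That may be a text-extraction fault and is not relied on. The transform figures above assume the standard form; the exact-tail figures do not depend on it. The cited pooling paper is not at hand and may say how the p-value is formed.

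The convention does not remove the point entirely. With the standard transform it gives about 2.64%, because the normal approximation is imperfect at 1 df.

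**Conclusion.** The point holds in a limited form. Section 4.2.4.2 carries no treatment direction into the pooled statistic, and neither natural reading delivers the declared 2.496%. Direct comparison gives about 1.3% for benefit (1.25% with exact tails) and lets a result favouring placebo formally open the next step. The conventional reading gives about 2.64%, an excess of roughly 0.14 percentage points. At the 0.001 level the conventional reading is slightly conservative instead (0.091%).

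The error rates rest on the standard Wilson-Hilferty form. The power figures rest on assumed reference powers, and the pooled results on assumed imputation settings. Severity is minor to should-fix: the intended direction can be inferred and a wrong-direction result would show in the win ratio, but the p-value gates two confirmatory endpoints and its decision rule should not be left to inference.

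**What to change.** Replace the Wilson-Hilferty step in 4.2.4.2. In each imputed dataset take the signed square root of the 1-df CMH statistic. The sign is that of the dapagliflozin minus placebo residual-score difference, combined over the T2D strata as in the CMH numerator, and the within-imputation variance is 1. Pool by Rubin's rule and compare the one-sided p-value favouring dapagliflozin with 0.02496, or with 0.001 after an early stop. The signed root is already approximately normal, so no transformation is needed.

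If the cited transform is kept, state that the pooled effect must favour dapagliflozin and that half the upper-tail p-value is compared with the one-sided level. Acknowledge the approximate 2.6% error, and check the formula's roots against the source file.

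Either change costs one or two sentences and about a line of code before unblinding. No new data are needed.

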4.2.5 Analysis of safety variables

Analysis set

For safety analyses, all summaries will be based on the safety analysis set (Section 2.1.2).

Exposure

The total exposure to study drug will be defined as the length of period on study drug, calculated for each patient as date of last dose – date of first dose +1.

An alternative measure where days of interruption are removed will be calculated and termed actual exposure.

Total and actual exposure will be presented descriptively.

Treatment periods

The summaries for the on-treatment period will include events with an onset date on or after first dose of randomized study drug and on or before 30 days after last dose of study drug. Additional presentations will include all events with onset on or after first dose of study drug regardless of whether patients are on or off study treatment at the time of the event (the ‘on +off ‘ treatment period).

All summaries of AEs and safety lab data described in Section 4.2.5.1 to 4.2.5.6 below will be presented for the on-treatment period. Additional summaries based on the on+off treatment period will be presented for SAEs and AEs of special interest. For fractures and amputations on+off treatment will be considered the primary analysis approach, while the on-treatment period will be the primary analysis approach for other AEs of special interest.

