1.1.3 Safety objectives

Safety Objective:
	
Outcome Measure :

To evaluate the safety and tolerability of dapagliflozin in this patient population.
	
 1. Serious Adverse Events (SAEs) 2. Discontinuation of IP due to Adverse Events (DAEs) 3. Changes in clinical chemistry/haematology parameters 4. Adverse events of interest (volume depletion, renal events, major hypoglycaemic events, fractures, diabetic ketoacidosis (DKA), AEs leading to amputation and AEs leading to a risk for lower limb amputations [“preceding events”])

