4.2.5.1 Adverse events

Summaries of AEs will primarily be based on the on-treatment period, except for fractures and amputations as described in section 4.2.5

In addition to SAEs, the collection of AEs that are not serious is limited to DAEs, AEs leading to interruption of IP or dose reduction and AEs of interest. Thus, summaries of AEs will be limited to these categories and general summaries of all AEs are not planned.

AEs will be classified according to MedDRA by the medical coding team at AstraZeneca data management centre, using the most current version of MedDRA possible.

Summaries by system organ class (SOC) and preferred term (PT) will be sorted by international order for SOC and by descending order of PT in the dapagliflozin treatment group.

No statistical tests to compare crude AE frequencies between treatment groups will be performed.

A summary table of the total number and percent of patients with SAE, DAE, AE leading to dose reduction and temporary interruption, and for each category of AE of interest per treatment group will be provided.

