4.2.5.2 Serious adverse events

SAEs will be presented as described below both on treatment and on+off treatment.

The number and percent of patients with SAEs will be presented by SOC, PT and treatment group. The most common SAEs will also be presented by PT and treatment group only.

AEs with outcome death will be presented separately by SOC and PT.

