4.2.5.3 Adverse events leading to discontinuation, interruption or dose reduction

The number and percent of patients will be presented by SOC and PT for AEs leading discontinuation, AEs leading to temporary interruption and dose reduction (separately for each of the three categories based action taken “Drug Permanently Discontinued”, “Drug Interrupted” and “Drug Reduced” respectively).

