4.2.5.4 Adverse events of interest

Each category of AEs of interest will be presented separately. AEs of interest fall in the categories volume depletion, renal events, major hypoglycaemic events, fractures, diabetic ketoacidosis (DKA), AEs leading to amputation and AEs leading to a risk for lower limb amputations [“preceding events”].

In addition to the pre-specified events of interest, analysis and presentation of potential events of Fournier’s gangrene will also be included.

Potential DKA events will be adjudicated. The adjudicated outcome will be considered the main analysis for DKA.

For each AE of interest, a summary table including the number and percent of patients with any event in the AE category, SAE, DAE, AE leading to interruption and dose reduction. Each AE of interest category will also be tabulated with frequency by PT.

In addition to presentations of the number of patients with event, the total number of events counting multiple events per patient will be presented for AE of special interest, where relevant eg for major hypoglycaemic events and amputation.

In addition to the presentation of on-treatment events, on+off presentations will be provided for all AEs of interest.

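### The overall DAE summaries are planned for the on-treatment period only, so an AE that leads to permanent discontinuation but starts more than 30 days after the final dose is not counted in them

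*SAP*

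**What the plan says.** Section 1.1.3 lists "Discontinuation of IP due to Adverse Events (DAEs" as the second outcome measure of the safety objective, and section 3.3 repeats DAEs among the safety variables. Under section 3.3, non-serious AEs that are DAEs are collected from randomization to the patient's last visit.

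Section 4.2.5 (Treatment periods) defines on-treatment events as those with onset from first dose to "on or before 30 days after last dose of study drug". It applies that period generally: "All summaries of AEs and safety lab data described in Section 4.2.5.1 to 4.2.5.6 below will be presented for the on-treatment period". The exception follows: "Additional summaries based on the on+off treatment period will be presented for SAEs and AEs of special interest". For fractures and amputations the on+off period is even the primary one.

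The subsections carry this out:
- Section 4.2.5.1: "Summaries of AEs will primarily be based on the on-treatment period, except for fractures and amputations". It also plans an overview table with a DAE row and says that no general summary of all AEs is planned.
- Section 4.2.5.2: "SAEs will be presented as described below both on treatment and on+off treatment".
- Section 4.2.5.3: "The number and percent of patients will be presented by SOC and PT for AEs leading discontinuation". The category is set by the recorded action, Drug Permanently Discontinued. No on+off version is mentioned.
- Section 4.2.5.4: "For each AE of interest, a summary table including the number and percent of patients with any event in the AE category, SAE, DAE", followed by interruption and dose reduction. On+off presentations are promised for all AEs of interest.

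**The concern.** A DAE is identified by what was done with study drug, whereas the on-treatment period is defined by when the AE began relative to the last dose. The two can come apart. The SAP expects interruptions: it removes interruption days from actual exposure and from the compliance denominator, and it has a separate Drug Interrupted category. A patient may be off drug during an interruption, have a new AE, and be taken off drug for good because of it. If that AE starts more than 30 days after what turns out to be the final dose, it is a DAE by action taken but falls outside the on-treatment period.

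At stake is the completeness of a named tolerability outcome. The restriction can only lower the DAE count, and the patients it removes are those already having difficulty staying on drug.

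**Working it through.** The SAP states no figure to reproduce. The check applies the window in section 4.2.5 to example dates (the days are assumed, the rule is the SAP's) and then traces where an excluded event would appear.

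**Step 1. When is a DAE excluded?** Window end = last dose day + 30. Interruption days between first and last dose are not carved out.

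| Case | Last dose | Window ends | AE onset | In the on-treatment DAE summaries? |
|---|---|---|---|---|
| (a) Interrupted at day 100, never resumed | 100 | 100 + 30 = 130 | 140 | No (140 > 130) |
| (b) Interrupted at day 100, resumed day 145, stopped for good day 150 | 150 | 150 + 30 = 180 | 140 | Yes (140 ≤ 180) |
| (c) Interrupted at day 100, never resumed | 100 | 130 | 125 | Yes (125 ≤ 130) |

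Exclusion therefore needs all three of: no resumption of dosing, onset more than 30 days after the final dose, and that AE being the one recorded with action Drug Permanently Discontinued.

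**Step 2. Where does an excluded event, as in case (a), still appear?**

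| Type of event | DAE table by SOC/PT (4.2.5.3) and DAE overview row (4.2.5.1) | Other planned AE tables |
|---|---|---|
| AE of interest, serious or not | Not counted | On+off AE-of-interest presentation, whose table includes a DAE count (4.2.5.4); also the on+off SAE table if serious |
| Serious, not an AE of interest | Not counted | On+off SAE table (4.2.5.2), not identified as a DAE |
| Neither | Not counted | None, because 4.2.5.1 plans no general AE summary |

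For the first row, section 4.2.5.4 does not spell out that the on+off presentation repeats every line of the table, but that is its natural reading.

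**Step 3. Direction.** Every on-treatment event is also an on+off event, since both periods start at first dose and only the first has an end tied to last dose. Hence the on-treatment DAE count can be at most equal to the on+off DAE count. The difference is the number of patients whose only DAE falls under case (a).

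**Step 4. Size.** The SAP gives neither a DAE rate nor the share of DAEs that start more than 30 days after the final dose. The difference cannot be computed from the document.

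**The case against.** The strongest defence is that the allocation of periods looks deliberate: on-treatment in general, on+off added for SAEs and AEs of interest, and on+off primary for fractures and amputations. The SAP does not contradict itself, and any on-treatment window lowers counts. An event that begins more than 30 days after the last dose is off-treatment by the plan's own definition. The window is the same in both arms of a double-blind trial, and section 4.2.5.1 plans no test of crude AE frequencies. Where an earlier AE caused the interruption, that AE is tabulated under Drug Interrupted, so the patient is not invisible. All of this stands. It shows a narrow coverage gap, not an error in the comparison of arms. It does not explain why DAEs, a named outcome defined by action taken, lack the additional period given to SAEs and AEs of interest. The word primarily in section 4.2.5.1 leaves room for an on+off DAE summary but commits to none.

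A reader might infer more than the text supports:
- That any DAE starting in a long interruption is lost. It is not: case (b) shows that resumed dosing moves the window later.
- That a late DAE is missing from every DAE count. Section 4.2.5.4 gives AEs of interest a DAE count and an on+off presentation.
- That the DAE total would fail to match patient disposition. The disposition text in section 4.1.5 concerns vital status and consent withdrawal; the SAP describes no disposition table by reason for stopping drug.

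**Conclusion.** The point holds in a limited form. As written, the DAE table in section 4.2.5.3 and the DAE row in section 4.2.5.1 omit an AE recorded as leading to permanent discontinuation if it starts more than 30 days after a last dose that is never resumed. Only an event that is neither serious nor an AE of interest is lost from all planned AE tables.

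The effect can only be downward. Its size is unknown and, given the conditions that must coincide, probably small. It is tempting to attach a number. With an assumed 5% DAE rate in 4500 / 2 = 2250 patients per arm (2250 × 0.05 = 112.5), and an assumed 2% to 10% of DAEs starting after the window, about 2 to 11 patients per arm would be affected (112.5 × 0.02 = 2.25; 112.5 × 0.10 = 11.25), or 0.1 to 0.5 percentage points. Only the 4500 comes from the SAP. Both percentages are assumptions, and the range includes events that would still be seen in the on+off SAE or AE-of-interest tables, so it is not evidence of size.

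No efficacy result is touched, and no bias between arms is shown. The reason to act is that a named outcome can be undercounted when the data to count it fully are already collected.

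**What to change.** In section 4.2.5, add DAEs to the sentence that lists the categories with additional on+off summaries. In sections 4.2.5.3 and 4.2.5.1, state that the DAE table by SOC and PT and the DAE row of the overview table will also be presented for all onsets on or after first dose, alongside the on-treatment version. The on-treatment table need not lose its primary place; which of the two leads is a matter of preference.

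The cost is a small text change and one extra table run, using a period the SAP already defines. The DAE percentage in the on+off version may be slightly higher than in the on-treatment version.
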